12-Apr-2023	Prior to final DB Lock	Major/Minor changes	
Final Amendment 2 (v2)
 
Major changes
 
 - Updated list of abbreviations - Tightened the study design with regards to Protocol Amendments, introduced terminology for treatment indications, clarified contradictory statements and removed duplicacy of information. - Distinguished efficacy and safety treatment groups for reporting on Part 1. Treatment indication precisely defined. - Precisely defined date of first/last administration of a study drug and study treatment - Corrected formula for Study day - Introduced different types of follow-ups as part of post-treatment period - Revised definition of Full analysis set - Revised definitions of IG analysis sets - Corrected the duration of exposure for Part 2 intermittent dosing - Aligned the organization of treatment indications with those mentioned Section 1.1.1 and Table 2-4 - Added a sentence to allow addition of any new qualifying treatment indication to inform the model. - Clarified that Secondary efficacy endpoints are to be evaluated in all Treatment groups contributing to primary efficacy objective. - Time to event endpoints to be estimated for trt groups >= 10 patients - Added precise definition of “sufficient” number of patients for change from baseline PSA analysis. - Clarified the criteria for summarizing efficacy endpoints for unknown RAS status. - Moved the paragraph on Safety summary from Section 2.1.1.5 to the right section under Section 2.6.2 - Tightened the reporting of AEs, SAEs, Deaths in line with the protocol with listings required on Screen failure patients. - Clarified that AESIs associated with combination trt will be reported using PDR001-specific eCRS . 	
 • List of abbreviations • Section 1.1 and sub-sections. • Section 2.1 • Section 2.1.1.2 • Section 2.1.1.3 • Section 2.1.1.5 • Section 2.2.1 • Section 2.2.4 • Section 2.4.1.1 • Section 2.5.2 • Table 2-4 • Section 2.5.2 • Section 2.6.1 • Section 2.6.1 • Section 2.6.1 • Section 2.6.1 • Section 2.6.2 • Section 2.6.2.1 • Section 2.6.2.2

Date	Time point	Reason for update	Outcome for update	Section and title impacted (Current)

This Statistical Analysis Plan (SAP) describes all planned analyses for the Clinical Study Report(s) (CSR) of study NIR178X2201, a phase II, multi-center, open label study of NIR178 in combination with PDR001 in patients with select advanced solid tumors and non-Hodgkin lymphoma (NHL).

The content of this SAP is based on NIR178X2201- Protocol Amendment 6. All decisions regarding interim analysis, as defined in the SAP document, have been made prior to database lock of the study data.

The output shells accompanying this document can be found in the Tables, Figures and Listings (TFL) shells document. The specifications for derived variable and datasets can be found in the Programming Datasets Specifications (PDS) document.

All changes to the planned analysis described in this document required before or after database lock will be made through an amendment or addendum, respectively. Note that obvious corrections will be made at the time of analysis to address minor formatting or spelling mistakes present in the TFL shells document without the need to amend.

The SAP, TFL shells, and PDS documents may also serve as a reference for the creation of any outputs required outside of the CSR, e.g., MTD/RD declaration, Investigator's Brochure (IB) updates, abstracts, posters, presentations, manuscripts, and management updates. Data used for these analyses will have a status aligned to the database lock guidance.

1.1 Study design

This is an open-label multi-part, phase II study evaluating the combination of NIR178 and PDR001 in patients with advanced solid tumors and diffuse large B cell lymphoma (DLBCL). Patients will receive combination treatment, NIR178 + fixed PDR001 400 mg Q4W, until disease progression (assessed by investigator as per iRECIST ([Appendix 3](#)) for solid tumors, [Cheson et al \(2014\)](#) for DLBCL or PCWG3 guidelines for mCRPC), unacceptable toxicity, start of a new anti-neoplastic therapy, or discontinuation at investigator's or patient's discretion, lost to follow-up, death or study termination by the sponsor. All patients who discontinue from study treatment due to disease progression must have their progression clearly documented. All disease assessments will be performed locally by the investigator. [REDACTED]

Note: For the rest of the document, PDR001 400 mg Q4W will be referred to as 'PDR001'; patients receiving single agent (SA) NIR178 as 'SA patients' and those receiving combination treatment as 'combination patients'.

[figure not shown]
This phase II study has 3 parts ([Figure 1-1](#)). Parts 1 and 2 will enroll patients in parallel, and consequent to results from the two parts, Part 3 will open in not more than two select study

indications once recommended dose and dosing schedule is determined. The study parts have the following objectives:

- **Part 1:** Multi-arm Bayesian adaptive signal finding design in groups of 13 treatment indications - 9 tumor types including DLBCL, with categories based on mutation status or prior IO treatment, and assigned continuous dosing of NIR178 (160 mg BID or following Protocol Amendment 5, 240 mg BID) in combination with PDR001.
Protocol Amendment 5 mandated administration of NIR178 240 mg BID + PDR001 in all newly enrolled patients having any of the Part 1 indications or 2 newly added indications, mCRPC and RCC IO-pretreated, leading to 13 groups (see Section 2.5.2).
- **Part 2:** Exploration of continuous and intermittent schedules of NIR178 160 mg BID in combination patients with advanced non-small cell lung cancer (NSCLC).
By the time Protocol Amendment 6 was formalized, this part was closed to enrollment and 'continuous' schedule was inferred as 'optimal'.
- **Part 3:** Further evaluation of 'optimal' NIR178 schedule (consequent to Part 2 results) in combination patients with selected Part 1 treatment indication.
Protocol Amendment 6 opened enrollment to Part 3 for exploring the safety and pharmacokinetics of the new FCT formulation of NIR178 160 mg BID at 'continuous' schedule in combination TNBC patients with PD-L1 SP-142 IC score of 0 (<1%). Provision to add another Part 1 treatment indication to Part 3, contingent on Part 1 analysis, was introduced as well.

[figure not shown]
In addition to the Phase II study, a safety run-in study will be conducted in Japanese patients with treatment indications specified in the Phase II study parts to evaluate the safety and pharmacokinetic profiles of NIR178 as a single-agent or in combination with PDR001 ([Figure 1-2](#)). As of Protocol Amendment 6, total 6 patients were treated - 3 with SA NIR178 80mg and 3 with SA NIR178 160mg, during Cycle 1 and with PDR001 initiated at the beginning of Cycle 2. This amendment required administration of NIR178 240 mg BID in combination with PDR001 among all newly enrolled Japanese patients. The dose escalation algorithm is detailed in Section 1.1.4.

Figure 1-11 Study design

- ¹Part 1: Bayesian adaptive signal finding in patients
- ²Prior to Amendment 5, all patients were treated with NIR178 160mg BID + PDR001 400mg Q4W
- ³Interim analysis of ORR using Bayesian adaptive model, Tumors in which treatment is not declared futile continue enrolling up to 30 patients (except for MSS CRC, 20 additional patients will be enrolled in each tumor group (RAS wildtype and RAS mutant))
- ⁴Part 2: NIR+PDR Schedule optimization
- ⁵Part 3: The selected groups will be based on emerging data from part 1, part 2 and latest scientific literature
- * Dose increment criteria to complete part 3 at 160mg BID or increase to 240mg BID

Figure 1-22 Study design- Japanese run-in part (NIR178 Single Agent and NIR178 +PDR001)

1.1.1 Part 1: Bayesian adaptive signal finding in solid tumors and DLBCL

Part 1 of the study will enroll patients in the combination arm with the following treatment indications and NIR178 BID doses (160 mg at the study beginning and 240 mg consequent to Protocol Amendment 5): renal cell carcinoma (RCC) - IO naïve (160 mg, 240 mg) and IO pretreated (240 mg), pancreatic cancer (160 mg), urothelial cancer (160 mg), squamous cell carcinoma of head and neck cancer (HNSCC) - IO naïve (160 mg) and IO pretreated (160 mg, 240 mg), microsatellite stable colorectal cancer (MSS CRC) - RAS wildtype (160 mg) and RAS mutant (160 mg), triple negative breast cancer (TNBC) (160 mg), cutaneous melanoma (BRAF V600E) (160 mg), diffuse large B-cell lymphoma (DLBCL) (160 mg, 240 mg), and metastatic castration resistant prostate cancer (mCRPC) (240 mg). Each indication will initially enroll at least 10 patients (with minimum requirements described in Protocol Section 4.2). Depending on whether or not pre-specified criteria for futility are met, each indication group may enroll up to a maximum of 30 patients with the exception of the MSS CRC RAS mutant and RAS wildtype groups, wherein 20 additional patients will be enrolled per group.

Accrual to each indication group in Part 1 will be based on futility assessment of observed ORR via non-binding interim analysis (IA) (explained below). The hierarchical model (see [Section 2.5](#)) is implemented to assess clinical significance of observed ORR, allowing dynamic borrowing of information between indications such that more borrowing occurs across those that have similar ORR and less borrowing occurs between those that differ. In this way, the model is a compromise between the two alternate extremes of either a completely pooled analysis or a separate analysis in each indication.

Note: For analysis, each of the indications - HNSCC IO pretreated & DLBCL, that has both 160 and 240 mg dose groups, was pooled into a single indication group due to limited observed responses, thus, maintaining the number of treatment indications contributing to the model to 13 that the study (Protocol Amendment 6) was designed for.

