10.4.2 Statistical hypothesis, model, and method of analysis

Part 1:

This part will contain thirteen groups: DLBCL at NIR178 160 mg BID, pancreatic cancer at NIR178 160 mg BID, HNSCC IO naive at NIR178 160 mg BID, urothelial cancer at NIR178 160 mg BID, RCC IO naive at NIR178 160 mg BID, TNBC at NIR178 160 mg BID, melanoma IO pretreated NIR178 160 mg BID, HNSCC IO pretreated NIR178 160 mg BID, MSS CRC RAS wildtype NIR178 160 mg BID, MSS CRC RAS mutant NIR178 160 mg BID, RCC IO pretreated at NIR178 240 mg BID, RCC IO naive at NIR178 240 mg BID, and mCPRC at NIR178 240 mg BID. All doses are given in combination with PDR001 400 mg Q4W. An adaptive Bayesian design ([Neuenschwander et al 2016](#)) will be used to assess activity of treatment in terms of overall response rate (ORR) within tumor type and across each tumor types.

The efficacy data from the Non-HNSCC patients, MSS CRC patients with unknown RAS status and IO naive melanoma patients will not be included in the statistical model. The design of the trial adapts to the data that are accumulated in the trial in such a way as to accommodate three possibilities:

- Scenario A: ORR is similar across tumor types
- Scenario B: ORR is similar for some tumor types and different in others
- Scenario C: The various tumor types have distinct ORR

The pre-specified analysis is adaptive in the sense that when response is similar across tumor types (Scenario A), then it borrows from across the various tumor types. In case some of the tumor types have similar ORR (Scenario B), the model provide more precise estimate of ORR rates for those tumor types with similar response rates by allowing borrowing only across these tumor types. In the other possibility (the various tumor types have distinct anti-tumor activity (Scenario C)); the design allows little/no borrowing across tumor types. In this case the trial will be similar to traditional stratified analysis.

A hierarchical model (HM) will be used to analyze the binary data to facilitate the borrowing as specified above. Response rates (π_j) will be inferred for tumor group j ($= 1, \dots, 13$). For each tumor type j , the number of responders follows a binomial distribution;

$$r_j \sim \text{Bin}(n_j, \pi_j)$$

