2.5.2 Statistical hypothesis, model, and method of analysis

2.5.2.1 Part 1

This part will contain thirteen groups: (1) RCC IO naive at NIR178 160 mg BID, (2) RCC IO naive at NIR178 240 mg BID, (3) RCC IO pretreated at NIR178 240 mg BID, (4) pancreatic cancer at NIR178 160 mg BID, (5) urothelial cancer at NIR178 160 mg BID, (6) HNSCC IO naive at NIR178 160 mg BID, (7) HNSCC IO pretreated NIR178 160 mg BID, (8) MSS CRC RAS wildtype NIR178 160 mg BID, (9) MSS CRC RAS mutant NIR178 160 mg BID, (10) TNBC at NIR178 160 mg BID (11) melanoma IO pretreated NIR178 160 mg BID, (12) DLBCL at NIR178 160 mg BID, and (13) and mCPRC at NIR178 240 mg BID.

Note: The efficacy data from the Non-HNSCC patients, MSS CRC patients with unknown RAS status and melanoma IO naive patients will not be included in the statistical model. The efficacy data from any new treatment indications added to the existing 13 groups before the study closure (as a consequence of Protocol Amendment 5) that qualify the criteria for Part 1 may be used to inform the model.

All doses are given in combination with PDR001 400 mg Q4W. An adaptive Bayesian design ([Neuenschwander et al 2016](#)) will be used to assess activity of treatment in terms of overall

response rate (ORR) within each and across treatment indications. The design of the trial adapts to the data that are accumulated in the trial in such a way as to accommodate three possibilities:

- Scenario A: ORR is similar across treatment indications
- Scenario B: ORR is similar for some treatment indications and different in others
- Scenario C: The various treatment indications have distinct ORR

The pre-specified analysis is adaptive in the sense that when response is similar across all treatment indications (Scenario A), then it borrows information from across all the various treatment indications. In cases when few of the treatment indications have similar ORR (Scenario B), the model provides more precise estimates of ORR rates for the treatment indications that have similar response rates by allowing to borrow information only across these treatment indications. In the other possibility when the various treatment indications have distinct anti-tumor activity (Scenario C), the design allows little/no borrowing of information across treatment indications. In this case the trial will be similar to traditional stratified analysis.

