Regarding the efficacy of part 3, [Table 3-5](#) shows the posterior mean and corresponding 95% credible interval for N=20 for various observed ORR rates using a minimally informative unimodal beta prior distribution with parameters $a=0.176$ and $b=1$ for TNBC patients (Note: this assumes a priori response rate of 15%). From [Table 3-5](#), with a sample size of 20 patients, if the observed ORR rate is 15%, the probability of true ORR rate for TNBC patients to be at least 13% is 54.8%

Table 3-5 Posterior mean and 95% credible intervals for given ORR rates

ORR (N, %)	Posterior mean (95% credible interval)	Probability of no improvement [0% - 5%]	Probability of limited improvement (5%-13%)	Probability of clinically meaningful improvement [13%-100%]
0(0%)	0.008 (0.00,0.066)	0.958	0.038	0.004
2 (10%)	0.103 (0.015, 0.259)	0.220	0.495	0.285
3 (15%)	0.150 (0.036, 0.326)	0.060	0.392	0.548
4 (20%)	0.197 (0.062, 0.386)	0.012	0.217	0.771
5 (25%)	0.244 (0.091, 0.443)	0.002	0.092	0.906
10 (50%)	0.481 (0.277, 0.688)	0.000	0.000	1.000

Japanese safety run-in part

The period for evaluating DLTs will be cycle 1 (i.e. the first 28 days of treatment with single agent NIR178 or in combination with PDR001). The safety run-in will evaluate three NIR178 dose levels sequentially. Each dose level may consist of 3 to 6 newly enrolled patients who have tumor histologies specified in Protocol Section 5, and who meet all other inclusion/exclusion criteria. The dose escalation strategy is detailed in [Section 1.1.4](#).

4 Change to protocol specified analyses

The study is closed out due to lack of sufficient efficacy and there is only TNBC indication opened in Part 3 at a single dose level - NIR178 160 mg BID. The dose increment criteria of Part 3 described in Section 1.1.3 will not be evaluated as no patients are enrolled at 240mg in Part 3.

5 Appendix

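### The SAP gives two definitions of the HNSCC-pretreated and DLBCL groups in the primary Part 1 model (both doses pooled because of few responses, or 160 mg only), and the final call can depend on which is run

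*SAP*

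**What the plan says.** The Note in SAP 1.1.1 concerns HNSCC IO-pretreated and DLBCL. It says that each indication "that has both 160 and 240 mg dose groups, was pooled into a single indication group due to limited observed responses", and adds that this keeps the model at 13 groups.

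SAP 2.5.2.1 specifies the primary model and lists its thirteen groups. Two of them read "7) HNSCC IO pretreated NIR178 160 mg BID" and "12) DLBCL at NIR178 160 mg BID". Protocol 10.4.2 agrees: "This part will contain thirteen groups: DLBCL at NIR178 160 mg BID", and later "HNSCC IO pretreated NIR178 160 mg BID, MSS CRC RAS wildtype NIR178 160 mg BID". The same SAP list keeps the second dose of another indication as its own group: "2) RCC IO naive at NIR178 240 mg BID".

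SAP 2.5.2.1 also says that data from indications added after Protocol Amendment 5 "that qualify the criteria for Part 1 may be used to inform the model". That sentence is permissive, and it does not mention merging doses within an indication.

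SAP Section 4, the place for departures from the protocol analysis, covers the study close-out and Part 3 only ("The dose increment criteria of Part 3 described in Section 1.1.3 will not be evaluated"). SAP 2.5.4 plans no sensitivity analyses. SAP 2.1 defines a treatment group as patients on the same treatment at the same dosage and schedule for the same indication.

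**The concern.** A programmer who follows SAP 1.1.1 fits different data from one who follows SAP 2.5.2.1. A third version is also open: the 240 mg patients could enter as extra strata under the permissive sentence. These data feed the primary endpoint (ORR) and a formal positive/negative rule.

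The stated reason for pooling is how many responses were seen. The trial is open-label, and SAP Section 4 says it closed for insufficient efficacy, so the grouping was fixed with results in view. If the choice of version can change the verdict, the verdict is not fully pre-specified. A positive result from a pooled group would also not show which dose it describes.

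**Working it through.** **Model (SAP 2.5.2.1; Protocol Appendix 4, Table 14-9).** For group j, r_j ~ Bin(n_j, π_j) and θ_j = logit(π_j). θ_j is N(μ1, τ1²) with weight 0.25, N(μ2, τ2²) with weight 0.25, and N(−2.197, 3²) with weight 0.50. The priors are μ1 ~ N(−1.735, 2.789²) and μ2 ~ N(0.405, 2.026²), with μ1 < μ2, and τ1, τ2 half-normal with scale 0.25.

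**Rule.** A group is positive if its posterior mean ORR ≥ C2 and P(ORR ≤ C1 | data) < 0.10. HNSCC-pretreated: C1 = 5%, C2 = 13%. DLBCL: C1 = 10%, C2 = 20%.

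**Reproducing the plan's figures.** I integrated over a grid in place of MCMC. All 52 rows of Protocol Table 14-19 (4 scenarios × 13 groups) agree: posterior means within 0.005 and probabilities within about 0.02 (largest gap 0.3595 against 0.3392). Two rows from scenario 4:
- DLBCL 7/30: 0.2119 / 0.0113, printed as 0.2111 / 0.0105.
- HNSCC-pretreated 6/30: 0.1937 / 0.0007, printed as 0.1944 / 0.0000.

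**Counts.** The 160 mg counts come from Protocol Table 14-18, scenario 1, which the protocol describes as its currently available data: HNSCC-pretreated 0/3 and DLBCL 1/10. The 240 mg counts are assumptions. All other groups are set to Table 14-19 scenarios 1 to 4 in turn.

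**Results** (posterior mean / P(ORR ≤ C1)):

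| Case | Sc. 1 | Sc. 2 | Sc. 3 | Sc. 4 | Call |
|---|---|---|---|---|---|
| HNSCC-pre, 160 mg only, 0/3 | 0.074/0.464 | 0.105/0.438 | 0.098/0.407 | 0.114/0.370 | negative ×4 |
| HNSCC-pre, pooled 0/3 + 3/10 = 3/13 | 0.177/0.025 | 0.230/0.010 | 0.202/0.010 | 0.208/0.005 | positive ×4 |
| HNSCC-pre, pooled 0/3 + 2/10 = 2/13 | 0.122/0.097 | 0.167/0.059 | 0.152/0.050 | 0.170/0.033 | negative on 1, positive on 2–4 |
| DLBCL, 160 mg only, 1/10 | 0.094/0.652 | 0.129/0.452 | 0.122/0.441 | 0.141/0.303 | negative ×4 |
| DLBCL, pooled 1/10 + 6/20 = 7/30 | 0.203/0.058 | 0.232/0.020 | 0.213/0.024 | 0.212/0.012 | positive ×4 (scenario 1 marginal) |

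The HNSCC-pretreated 3/13 means exceed 0.13 by 0.047 to 0.100, far more than the 0.005 reproduction error. The DLBCL scenario 1 margin (0.203 − 0.200 = 0.003) lies within that error. Dropping μ1 < μ2 moves the pooled and 160 mg-only means by at most 0.002 and changes none of those verdicts.

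**Pooling can also hide a signal.** Take DLBCL 1/10 at 160 mg and 3/10 at 240 mg, on scenarios 3 and 4. Pooled 4/20 gives 0.183/0.104 and 0.190/0.054, negative. The 240 mg patients as their own stratum give 0.242/0.065 and 0.236/0.035, positive. On scenario 1 both versions are negative (pooled 0.161/0.228, own stratum 0.228/0.151). On scenario 2 both are positive (pooled 0.201/0.098, marginal; own stratum 0.272/0.051).

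**Wider sweep, 160 mg only against pooled.** I assumed sizes of 10 + 10 for DLBCL and 14 + 10 for HNSCC-pretreated, with 0–4 responders at 160 mg and 0–3 at 240 mg (5 × 4 = 20 splits). In each indication, 4 of the 20 splits change the call on every scenario, and changes occur in both directions. For DLBCL on scenario 3, 3/10 + 0/10 is positive as 160 mg only (0.248/0.060) and negative when pooled (0.149/0.230).

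**Where nothing changes.** Starting from 0/3 and 1/10 at 160 mg, with 0/10 or 1/10 at 240 mg, every version of both groups is negative on all four scenarios.

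**The case against.** The strongest reply is that SAP 1.1.1 states a definite decision, specific to these two groups, and that the 160 mg labels in 2.5.2.1 are simply carried over from the protocol. SAP Table 2-4 puts no dose on either row, so it does not contradict pooling. The change log says that Section 2.1 now separates efficacy from safety groupings, and a blacked-out bullet there may hold the governing rule. That may be so, but a redacted rule cannot make 1.1.1 and 2.5.2.1 agree.

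RCC-naive at 240 mg is separate because the protocol made it so after an interim decision; the protocol created no such group for the other two indications. That weakens the RCC comparison but leaves the contradiction untouched.

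The changes of verdict above need 20–30% response at 240 mg, which fits poorly with few responses and closure for insufficient efficacy. This limits the claim to what could happen.

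The 0/3 count is an interim snapshot. The Amendment 5 status gives 23 − 4 = 19 HNSCC patients, against 9 + 3 = 12 in scenario 1. If 160 mg were 0/10 (assumed) with 3/10 at 240 mg, pooled 3/20 is negative on scenario 1 (0.123/0.058) but positive on scenarios 2–4. With 2/10 at 240 mg, pooled 2/20 is positive only on scenario 4, and only just (0.133/0.084). The result therefore depends on this input, but a change remains possible.

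Finally, the work is exploratory, and no visible passage proposes a dose-specific claim from a pooled group. That bears on how much to ask for, and the extra fits are cheap.

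**Conclusion.** The concern holds. The visible text gives two incompatible definitions of two groups in the primary Part 1 model. One is justified by the observed responses, and the pooling is neither logged as a change nor covered by a sensitivity analysis. Confidence is high on the contradiction and on the fact that the choice can decide the call: HNSCC-pretreated at 0/3 + 3/10 moves from negative to positive on all four scenarios. It is not shown that the actual verdict changed. The 240 mg counts are assumed, the 160 mg counts are interim, and with very few responses all versions agree on a negative result. This should be fixed before the results are interpreted.

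**What to change.** - Make SAP 1.1.1, 2.5.2.1 and Table 2-4 state one grouping rule for these two indications that does not rest on observed responses.
- Replace the permissive sentence on added indications with a fixed rule.
- Beside any pooled result, report (i) the 160 mg-only fit listed in the protocol and (ii) a dose-separated fit, with the 240 mg HNSCC-pretreated and 240 mg DLBCL patients as their own strata and the same C1 and C2, as is done for RCC-naive. Put both fits in 2.5.4.
- Record the pooling in Section 4, with its date and reason.
- Make no positive claim for a particular dose from a pooled group alone.

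The cost is SAP wording and two more runs of an existing program. The small 240 mg strata will have wider credible intervals, and there is more output to explain. The dose-separated fit is itself post hoc, so it should stand beside the pooled result and not replace it.
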